Transcranial Direct Current
Stimulation for Post-stroke Gait
Rehab

NCT03666533

July 13, 2023

Simultaneous transcranial direct current stimulation and gait training for chronic stroke
NCT 03666533

Abbreviated Protocol (from last IRB approved version - 07/2023)

SPECIFIC AIMS Gait deficits following stroke are prevalent and frequently persistent after stroke. Current rehabilitation methods fail to restore normal gait for many stroke survivors. Those who have persistent gait deficits following stroke even after intensive rehabilitation efforts tend to be more dependent on caregivers for assistance with ADLs, demonstrate limitations in household and/or community ambulation, are at higher risk for falls, and report poor quality of life (QOL). One promising treatment method that warrants further investigation is transcranial Direct Current Stimulation (tDCS), a form of non-invasive brain stimulation (NIBS). If found to be effective, tDCS is readily deployable into the neurorehabilitation clinical setting because of its safety, ease of set-up and ability to be paired with other established and effective gait rehabilitation methods. The purpose of this current study is to develop treatment methods that improve gait for those with persistent deficits following stroke. In the proposed study, we will compare the response to active tDCS+gait training versus sham tDCS +gait training. Gait training will be provided within a virtual reality (VR) gait training system and overground and will ensure a consistent, repeated motor learning-based pattern of practice. AIM 1: Determine whether the combination of simultaneous tDCS and gait training produces superior improvement in gait performance than gait training alone. Hypothesis 1: There is an additive advantage in combining tDCS and gait training in improving gait performance in chronic stroke survivors. AIM 2: Characterize the neuroplastic brain changes in response to bihemispheric tDCS combined with gait training. Hypothesis 2: The combination of gait training and tDCS results in a greater increase in corticospinal excitability and strengthened functional connectivity compared with gait training alone. AIM 3: Identify factors that predict gait improvement in response to tDCS with gait training. Hypothesis 3a: Greater gait improvement in response to bihemispheric tDCS with gait training is related to the following combination of baseline factors 1) corticospinal tract (CST) lesion load; 2) greater motor abilities of the affected lower extremity; 3) greater corticospinal excitability; 4) greater functional connectivity; 5) higher integrity of the stroke-affected corticospinal tract; and, 6) lesion type (cortical, subcortical, brain stem). Hypothesis 3b: Greater gait improvement in response to bihemispheric tDCS is dependent on the tDCS-induced electrical current density at the targeted cortical areas in the primary motor cortex for lower extremities.

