
Study design overview This study is testing the efficacy of utilizing tDCS during gait training for individuals with chronic stroke (>6 mo post-stroke) who demonstrate an abnormal gait pattern. This is a randomized controlled multi-session study to test the potential benefit of combining tDCS and gait training for individuals with chronic gait deficits after stroke. The key exclusion criteria will be more than one stroke, contraindications for transcranial magnetic stimulation, and presence of implanted medical devices such as cardiac pacemaker or vagus nerve stimulator. .

Study intervention Subjects participated in 10 treatment sessions, a baseline testing (includes MRI), a mid-treatment testing session, a testing session after the 10th treatment session (includes MRI) and a 6-week follow-up testing visit. Clinical outcome measures were collected by a trained study staff who is not involved in therapy and blinded to group allocation. Subjects will be randomly allocated to either Treatment Group 1) active tDCS+gait training or Treatment Group 2) sham tDCS+gait training. Each VR gait training session lasted 30 minutes and tDCS will be “on” for the first 15 minutes while the subject simultaneously participates in gait training with guidance of a study physical therapist. Immediately after VR+tDCS training,

subjects participated in 30 minutes of overground training guided by a physical therapist. Home exercises were assigned to be completed on non-training days and reinforced in-person therapy training. Both, the subject and the study staff who is delivering therapy were blinded to group allocation.

Aims 1 and 2 analysis: We directly compare pre to post changes for gait speed and paretic single limb stance duration between the two groups. Similarly, secondary outcome measure changes are being compared between the study groups. We compare trajectories of changes in primary and secondary outcome measures afforded by longitudinal measurement through the course of study participation, using mixed models and the analysis of Treatment Group by time interaction effects. Time is considered as a categorical variable as well as modeled with random slope parameters. Two-sample comparisons of change values are conducted with t-tests or nonparametric methods such as Mann-Whitney U tests.

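### The Aim 1 gait comparison has no designated deciding analysis, and none of the analyses listed for it adjusts for baseline, although the baseline data needed are already collected

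*Combined protocol and SAP*

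**What the plan says.** Aim 1, under Specific Aims, is worded as "AIM 1: Determine whether the combination of simultaneous tDCS and gait training produces superior improvement in gait performance than gait training alone". It names no outcome, time point or test.

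Study intervention sets four assessments: a baseline test, then "a mid-treatment testing session, a testing session after the 10th treatment session (includes MRI) and a 6-week follow-up testing visit".

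The Aims 1 and 2 analysis section then lists several treatments of the same data:

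- A change comparison: "We directly compare pre to post changes for gait speed and paretic single limb stance duration between the two groups".
- The tests for it: "Two-sample comparisons of change values are conducted with t-tests or nonparametric methods such as Mann-Whitney U tests". No rule is given for choosing between them.
- Longitudinal models: "We compare trajectories of changes in primary and secondary outcome measures", "using mixed models and the analysis of Treatment Group by time interaction effects".
- Two ways of handling time in those models: "Time is considered as a categorical variable as well as modeled with random slope parameters".

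The section does not call gait speed and stance duration primary in so many words. That is inferred from the next sentence, which turns to the secondary measures. No baseline covariate, ANCOVA or common baseline mean is mentioned for the treatment comparison. Baseline variables enter a model only in the Aim3 analysis, as predictors of change. The document describes itself as an abbreviated protocol.

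**The concern.** There are two linked problems. First, the same two gait outcomes will be analysed in several ways, and the text does not say which result answers Aim 1. A reader of the final report could not tell whether the reported analysis was the intended one.

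Second, every analysis as described works from unadjusted change. In a randomised trial with a baseline measurement of the same variable, adjusting the post value for baseline is normally at least as precise as subtracting it, and it also corrects for chance baseline imbalance. The plan has the data and leaves this gain unused. The mixed model might seem to supply the adjustment, but as described it does not.

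**Working it through.** **Inputs.** The documents give no sample size, alpha, effect size, SD or correlation, so there is no figure to reproduce. Assumed here: two-sided 5%, 1:1 allocation, baseline-to-post correlation rho of 0.5 to 0.9, post/baseline SD ratio k of 0.8 to 1.25, and 10 to 40 per group.

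**Step 1: does the categorical-time model adjust for baseline?** With a separate mean for each group at each visit, complete data and unstructured covariance, the fitted means are the observed means. The interaction contrast at post is therefore (active post − active baseline) − (sham post − sham baseline), the unadjusted difference in change. In 4,000 simulated trials (20 per group, rho 0.7, four visits) the largest discrepancy was 3e-15.

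**Step 2: would adding baseline as a covariate to that model help?** No. A covariate constant over visits adds the same amount at baseline and at post, and cancels from the contrast. In one simulated trial the contrast was −0.5501 with the covariate, identical to the unadjusted change difference, against −0.4903 for ANCOVA. Giving both groups a common baseline mean does work: in the 4,000 trials that contrast matched ANCOVA to within 3e-15.

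**Step 3: what does adjustment gain in large samples?** In units of the baseline variance, change has variance 1 + k² − 2·rho·k, and post given baseline has k²(1 − rho²).

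Ratio = k²(1 − rho²) / (1 + k² − 2·rho·k). At k = 1 this is (1 + rho)/2.

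| rho | k = 0.8 | k = 1 | k = 1.25 |
|---|---|---|---|
| 0.5 | 0.57 | 0.75 | 0.89 |
| 0.7 | 0.63 | 0.85 | 0.98 |
| 0.8 | 0.64 | 0.90 | 1.00 |
| 0.9 | 0.61 | 0.95 | 0.95 |

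The range is about 0.57 to 1.00. The value 1.00 arises where rho·k = 1, that is 0.8 × 1.25.

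If the change-score test has 80% power, its noncentrality is 1.960 + 0.842 = 2.802. Dividing by the square root of the ratio at k = 1:

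- rho 0.5: 2.802/√0.75 = 3.235, power 90%
- rho 0.7: 2.802/√0.85 = 3.039, power 86%
- rho 0.9: 2.802/√0.95 = 2.875, power 82%

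**Step 4: small samples.** Using the noncentral t with 2n − 3 degrees of freedom, averaged over chance baseline imbalance, 80% becomes 89%, 85% and 81% with 20 per group, and 88%, 84% and 79% with 10 per group.

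Estimating the baseline slope inflates the ANCOVA variance by 1 + 1/(2n − 4). At k = 1 the break-even rho is 2/(1 + 1/(2n − 4)) − 1, which is 0.88, 0.95 and 0.97 at 10, 20 and 40 per group. If the post SD is 10% larger than baseline, break-even at 10 per group falls to about 0.74. The variance penalty is nevertheless never more than the factor itself, 1.0625 at 10 per group.

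**Step 5: can the listed analyses disagree?** This depends on a choice that the text does not make. Simulations used one outcome and rho 0.7.

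- If the interaction is a 3-df omnibus test over the three follow-up visits, the chance under no effect that at least one of t-test, Mann-Whitney and interaction has p < 0.05 is about 9%. With 80% power for the t-test and 20 per group, t-test and omnibus test disagree in roughly 15–18% of trials, and up to about 22% depending on how the omnibus test is computed.
- If the interaction is the post contrast alone, the any-positive chance is 5.7% to 6.4% and disagreement with the t-test is 0% to 4%.

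**Step 6: two outcomes.** If success on either outcome met Aim 1, each tested at 5%, the error would be up to 1 − 0.95² = 9.75% with independent outcomes. If both had to succeed, there would be no inflation.

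**The case against.** The best reply is that the plan is valid as it stands. Change-score comparisons are unbiased under randomisation, the pre-to-post comparison is listed first and may be meant to lead, and a fuller protocol may rank the analyses. The gain from adjustment is modest, is absent for some combinations of rho and SD ratio, and can reverse slightly in a very small trial. All of this stands, and it limits the point to precision and clarity. It does not remove it: order of mention is not designation, and a leading change comparison would still be unadjusted, with its test left open.

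Three stronger readings are tempting and are not supported:

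- *That baseline is ignored or the comparison is biased.* Change from baseline uses the baseline value; it does not adjust for it.
- *That the plan carries a 9% false-positive rate or a 15–18% chance of contradictory answers.* Those figures assume the omnibus interaction test. The text refers only to interaction effects and specifies no such test.
- *That the random-slope model gives the post test almost no weight.* That would need a linear fixed time term in weeks, an assumed training length and an assumed origin for the 6-week visit. The text gives none of these, and with categorical fixed time plus random slopes the problem does not arise. No power figure for the slope analysis is therefore offered.

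**Conclusion.** The point holds as a worthwhile, inexpensive improvement, and the planned inference remains valid. In the supplied text no analysis is named as deciding Aim 1, and none of those listed is baseline-adjusted; the categorical interaction contrast reduces to the unadjusted change difference with complete data and unstructured covariance. The likely cost is a variance that is higher than necessary: adjustment would bring it to 75–95% of the change-score variance at equal SDs and rho of 0.5 to 0.9, worth about 2 to 10 points of power from 80% in large samples. For SD ratios of 0.8 to 1.25 the ratio runs from about 0.57 to 1.00. Where this trial lies cannot be determined, because sample size, correlation and SDs are not given. The missing designation is mainly a gap in detail, which a fuller protocol may already fill.

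**What to change.** For each of the two gait outcomes, make the baseline-adjusted active-minus-sham contrast at the post-treatment test the deciding Aim 1 analysis. Either of two models gives it:

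- the planned categorical-time model with a common baseline mean for both groups and unstructured covariance; or
- a model with baseline removed as a response and entered as a covariate, with a baseline-by-visit term.

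Adding baseline as a covariate to the four-visit model is not enough (Step 2). For outcomes measured only at baseline and post, use ANCOVA of post on baseline.

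Also state whether one or both outcomes must succeed for Aim 1, and how error is controlled if either suffices. Treat the 6-week contrast as retention, and the t-test, Mann-Whitney and random-slope analyses as supportive. The text mixes past and future tense, so analysis may be under way; if unblinded results have been seen, label the choice as made afterwards.

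The cost is wording and a small change to the model, with no new visits or data, plus one degree of freedom. With equal SDs that degree of freedom matters only at very high correlation in a small sample (break-even rho 0.88 at 10 per group). If a fuller protocol already names the deciding analysis, carry that statement across and add the baseline adjustment.

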Aim3 analysis: We correlate change in clinical gait performance measures in response to intervention with baseline variables describing the structural integrity of the corticospinal tracts, functional brain connectivity and lower limb motor abilities. We also explore regression analyses where changes in gait measures is modeled as a dependent variable, and include predictors such as baseline TMS measures (MEP-rc), DTI measures, functional connectivity, motor ability measure and electrical field estimate values.

Inclusion and Exclusion Criteria

Inclusion criteria

- Medically stable and at least 6 months after first ever stroke
- Cognition sufficiently intact to give valid informed consent
- Ability to follow two stage commands.
- Sufficient endurance to participate in the study.
- Age >18
- Observable stance gait deficit while walking on level surface.

Exclusion Criteria

- Acute or progressive cardiac, renal, respiratory, neurological disorders or malignancy.
- Any psychiatric diagnosis or active psychological condition
- More than one ischemic stroke or stroke affecting both sides
- Lower motor neuron damage or radiculopathy
- No observable gait deficit during ambulation
- Presence of implanted medical devices such as cardiac pacemakers and defibrillators, intrathecal drug delivery pumps, or spinal cord, vagus nerve or similar stimulators, or cochlear implants
- Presence of metallic hardware in close contact with the TMS coil such as intracranial implants, aneurysm clips, plates, electrodes
- Past history of seizures or unexplained loss of consciousness
- Family history of medication refractory epilepsy
- History of substance abuse within the last 6 months

- Chronic sleep deprivation, ongoing untreated sleep disorder
- Pregnancy or pregnancy planning during the study period
- Inability to understand English.
- Activity tolerance insufficient to complete VR treadmill training.

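### Aim 3 relates gait change to baseline factors without specifying adjustment for baseline gait, so associations for factors that track baseline gait can be distorted in either direction

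*Combined protocol and SAP*

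**What the plan says.** The Aim3 analysis paragraph has two parts. The first is a set of simple correlations: "We correlate change in clinical gait performance measures in response to intervention with baseline variables". The variables are "baseline variables describing the structural integrity of the corticospinal tracts, functional brain connectivity and lower limb motor abilities". No covariate is named.

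The second is worded as exploratory: "We also explore regression analyses where changes in gait measures is modeled as a dependent variable". The models will "include predictors such as baseline TMS measures (MEP-rc), DTI measures, functional connectivity, motor ability measure and electrical field estimate values". The baseline value of the gait measure is not named, but the list is given as examples and is not closed.

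Hypothesis 3a, in the Specific Aims, ties greater gait improvement to six baseline factors. Four have a stated direction, all positive: motor ability ("greater motor abilities of the affected lower extremity"), corticospinal excitability, functional connectivity and integrity of the affected tract. Lesion load and lesion type have none.

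The Aims 1 and 2 analysis paragraph names the gait measures: "We directly compare pre to post changes for gait speed and paretic single limb stance duration between the two groups". Baseline gait must therefore be collected. The document does not mention baseline-gait adjustment or regression to the mean for Aim 3.

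**The concern.** Change is post minus pre, so the covariance of any factor with change includes minus its covariance with baseline gait. Motor ability, excitability, connectivity and tract integrity can all plausibly be expected to go with better walking at entry. For such a factor, an unadjusted association with change mixes two things: whether the factor predicts response, and whether it merely follows how well the patient already walks.

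Aim 3 is meant to identify predictors, with signs stated in advance. Without a baseline-adjusted analysis, a true predictor may be masked, or a factor that carries nothing beyond baseline gait may appear to predict. Because the regression list is open, baseline gait could also be added or left out after the results are seen. The point concerns Aim 3 only and leaves the randomised comparison in Aim 1 untouched.

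**Working it through.** The plan states no figure for Aim 3, so there is none to reproduce. The structure comes from the Aim3 analysis paragraph; every number below is an assumption.

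**Notation.** SD(pre) = 1, SD(post) = k, rho = corr(pre, post), r = corr(factor, pre). SD(change) = sqrt(1 + k² - 2·rho·k).

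**1. Identity.** Cov(factor, change) = Cov(factor, post) - Cov(factor, pre).

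**2. Factor with no information beyond baseline gait.** Here corr(factor, post) = r·rho, so

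corr(factor, change) = r·(rho·k - 1) / sqrt(1 + k² - 2·rho·k).

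The sign is that of rho·k - 1: negative when rho·SD(post) < SD(pre), positive when it is greater.

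With r = 0.6:

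| rho | k = 1.0 | k = 1.1 | k = 1.2 |
|---|---|---|---|
| 0.95 | -0.09 | +0.08 | +0.21 |
| 0.90 | -0.13 | -0.01 | +0.09 |
| 0.80 | -0.19 | -0.11 | -0.03 |
| 0.70 | -0.23 | -0.17 | -0.11 |

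Example, k = 1 and rho = 0.80: 0.6 × (-0.20) / sqrt(0.40) = -0.12 / 0.632 = -0.19. A simulation of one million draws at r = 0.5, rho = 0.80, k = 1 gave -0.157 against -0.158 from the formula.

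By Fisher's z, with 40 patients (assumed) and two-sided 5%, the four values in the k = 1.0 column would be significant about 9%, 13%, 22% and 30% of the time.

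**3. Factor with real information beyond baseline gait.** Let the partial correlation with post given pre be 0.40, with r = 0.6 and k = 1. Then corr(factor, post) = r·rho + 0.40·sqrt((1 - r²)(1 - rho²)).

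- rho = 0.90: 0.54 + 0.40 × 0.349 = 0.679; with change, (0.679 - 0.600) / 0.447 = 0.18.
- rho = 0.80: 0.48 + 0.40 × 0.480 = 0.672; with change, (0.672 - 0.600) / 0.632 = 0.11.

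Power at 40 patients is about 19% and 11%, against 72% for the test of the partial correlation. With k = 1.1 the unadjusted power is 49% and 25%.

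**4. The opposite case.** Suppose true gait is stable, pre and post differ only by independent measurement error, and the factor correlates 0.6 with true gait. Then Cov(factor, change) = 0 and the unadjusted correlation is unbiased. With reliability R, corr(factor, pre) = corr(factor, post) = c = 0.6·sqrt(R), and corr(pre, post) = R. The partial correlation given observed baseline is c(1 - R) / sqrt((1 - c²)(1 - R²)).

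- R = 0.95: 0.585 × 0.05 / sqrt(0.658 × 0.0975) = +0.12.
- R = 0.80: 0.537 × 0.20 / sqrt(0.712 × 0.36) = +0.21, significant about 25% of the time at 40 patients.

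In this case the adjusted result is the spurious one, and it favours Hypothesis 3a.

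**The case against.** **The direction is not fixed.** A reader might infer that omitting baseline gait necessarily pulls motor ability and similar factors against Hypothesis 3a. The documents do not support that. It needs rho·SD(post) < SD(pre) and a factor that follows observed baseline gait; no SDs or correlations are given. If gains are unrelated to baseline, there is no pull, and if spread widens enough it reverses. This objection stands, and the point is worded conditionally for that reason.

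**Adjustment is not neutral.** Step 4 shows a bias as large as the one in step 2 and favourable to the hypothesis. Nothing in the documents says which error structure applies. This also stands, and it rules out simply replacing the planned correlations.

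**The two analyses answer different questions.** Aim 3 asks which factors predict improvement, not improvement beyond baseline gait, and the unadjusted association is a legitimate answer to who improves. The power contrast in step 3 is partly by construction, since the effect is defined as a partial correlation. That is fair; the reply is that the plan should say which question each result answers.

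**The list is open, the regression exploratory and the protocol abbreviated.** A reader might infer that baseline gait is excluded; the wording does not say so. But the open list covers only the regression. The simple correlations come first and name no covariate, and identifying predictors is a numbered aim with directional hypotheses.

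**Conclusion.** The point holds in conditional form. Aim 3 does not specify the baseline value of the gait measure in either its correlations or its regressions, so the association of change with a factor that tracks baseline gait can be distorted, toward the negative or the positive depending on rho and the SD ratio. Under equal SDs and a factor-baseline correlation of 0.6, an uninformative factor shows about -0.09 to -0.23; with post SD 10% to 20% larger, the same factor ranges from -0.17 to +0.21 over the same pre-post correlations. These sizes illustrate and do not estimate what this trial will show. The documents do not support saying that Aim 3 will hide true predictors or give them the wrong sign, only that it may, and that the planned analysis alone could not reveal it.

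**What to change.** For each Aim 3 factor, keep the planned correlation with change and report beside it a baseline-adjusted analysis: post-treatment gait (or change) on the factor plus the baseline value of the same gait measure, or the equivalent partial correlation. State this before the Aim 3 results are examined. Claim that a factor predicts improvement beyond baseline gait only from the adjusted result, and treat it as a robust predictor only if the two analyses agree in direction.

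The cost is one degree of freedom per model and a few sentences; no new data are needed. The downside is the positive bias from an error-prone baseline shown in step 4, which should be stated with the results.

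### Does the word ischemic in the stroke-history exclusion leave the eligibility rule contradicting the design overview?

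*Combined protocol and SAP*

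**What the plan says.** Three statements in the combined protocol and SAP bear on stroke history.

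- The Study design overview: "The key exclusion criteria will be more than one stroke, contraindications for transcranial magnetic stimulation". It limits neither the type nor the side of the strokes. It describes the population as "individuals with chronic stroke (>6 mo post-stroke) who demonstrate an abnormal gait pattern".
- The Inclusion criteria: "Medically stable and at least 6 months after first ever stroke".
- The Exclusion Criteria: "More than one ischemic stroke or stroke affecting both sides".

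A separate exclusion, "Acute or progressive cardiac, renal, respiratory, neurological disorders or malignancy", together with the stability requirement in the inclusion line, covers a recent unstable event. Hemorrhagic stroke as such is excluded nowhere. The document describes itself as an abbreviated protocol drawn from the last approved version of July 2023.

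**The concern.** The overview and the exclusion bullet are both current text, and they do not cover the same patients. The overview rules out any second stroke. The bullet rules out a second ischemic stroke and strokes on both sides, so a same-side second stroke that is not part of an ischemic pair falls outside it. The inclusion line, read strictly, sets a minimum time since the first stroke. It does not in so many words bar a later one, nor does it say which stroke starts the six-month clock.

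If two sites or two screeners read these lines differently, the trial could hold a few participants with two strokes. Three things would then be at stake:

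- the description of the population to which the gait comparison applies;
- some added spread in gait change;
- in Hypothesis 3a, the coding of a three-level lesion-type variable and of corticospinal tract lesion load when there are two lesions.

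**Working it through.** The plan states no figure on this point, so the check is to apply each rule to each possible history.

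**Histories.** Two strokes can be both ischemic, mixed, or both hemorrhagic (3 combinations), and on the same side or on both sides (2 patterns): 3 × 2 = 6. These are logical cases, not patients.

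| History | Overview | Exclusion bullet alone | Inclusion line, first-stroke reading |
|---|---|---|---|
| Both ischemic, same side | out | out | out |
| Both ischemic, both sides | out | out | out |
| Mixed, same side | out | not named | out |
| Mixed, both sides | out | out | out |
| Both hemorrhagic, same side | out | not named | out |
| Both hemorrhagic, both sides | out | out | out |

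**Bullet against overview.** The overview excludes 6 and the bullet 1 + 3 = 4, leaving 6 − 4 = 2 in conflict. If the words about both sides meant only a single stroke with bilateral damage, the bullet would exclude just the two ischemic pairs, leaving 6 − 2 = 4.

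**All criteria together.** A patient must meet every inclusion criterion and no exclusion criterion. A bullet that does not name a patient does not admit that patient. If the first ever stroke is the qualifying and only stroke, the inclusion line excludes all 6 and the conflict with the overview is 6 − 6 = 0, whichever way the bullet is read. The six-month question also disappears, because there is only one stroke to count from.

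**A single bilateral stroke.** The bullet excludes it and the overview does not mention it. That is no contradiction, since the overview claims to give only the key exclusions.

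**Effect on the analyses if a two-stroke patient did enter.**

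- *Aims 1 and 2.* Stroke history predates random allocation and cannot depend on it. Such patients could add noise but would not favour an arm systematically. The change comparisons and the mixed models would run as written.
- *Aim 3.* One stroke can involve both cortical and subcortical tissue, so a three-level lesion variable needs a coding rule even in a strictly single-stroke sample. The Aim3 analysis text offers its regressions as exploratory, and its list of predictors, given as examples, does not name lesion type or lesion load.

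**Timing.** The Study intervention section reports treatment in the past tense ("Subjects participated in 10 treatment sessions"), although it uses the future tense for allocation. Enrolment may therefore be over, in which case rewording the bullet would alter nobody's eligibility.

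**The case for a change.** The best argument for acting is that the word ischemic looks deliberate. Calling the overview's list key explains why it leaves criteria out, but not why it states a wider exclusion than the formal list. And if the inclusion line already meant one stroke only, a bullet about multiple ischemic strokes would be unnecessary; confining it to ischemic strokes invites the inference that other second strokes are acceptable.

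The first part stands: the wording differs, and the summary label does not explain it. The redundancy argument is weaker, because these lists repeat themselves elsewhere. A visible gait deficit is required for inclusion and its absence is then an exclusion; adequate endurance is required and inadequate tolerance of treadmill training is then excluded. A bullet that partly restates an inclusion criterion fits that habit.

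A narrower case survives on the strict reading: a stable second stroke on the same side, not part of an ischemic pair and less than six months old. But the overview bars that patient twice, through its single-stroke rule and through its definition of the population as chronic. It is a possibility on paper, with nothing in the documents to suggest that it occurred.

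It is also fair to say that checking stroke histories would cost little. Low cost is not a gain in itself, however, and no result in the plan has been shown to depend on the answer.

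**Conclusion.** The mismatch is real but clerical. Two of the three statements, the overview and the inclusion line in its ordinary sense, describe a single-stroke population; the third is a bullet drafted too narrowly. At most it leaves unnamed two of six two-stroke histories, or four on the narrowest reading of the bilateral wording, and none once the criteria are applied together with the inclusion line taken as a first-stroke requirement.

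This rests on two assumptions: that screeners read the inclusion line in that usual way, and that they applied all the criteria jointly. If the first fails, a few two-stroke patients could have been enrolled. The consequence would be some extra variability in gait change, without bias between the arms and without effect on any test or stated figure. The number of such patients cannot be estimated from the documents. Because the source is abbreviated, the wording that screeners actually used may also have been fuller. An analyst following the plan as written would still reach sound conclusions, and an ordinary baseline description of stroke history would show whether the question ever arose. No change to the plan is needed.
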